- In-person MTM (required only of pharmacists randomized to MTM + PGx testing arm): The purpose of this CE is to review elements of MTM, development of medication action plans, and incorporation of PGx testing into an MTM session. The development of this module was adapted from the MTM module offered by the American Pharmacists' Association (APhA). Attendance may be waived if the pharmacist provides proof of completion of the APhA MTM CE program.

PART II. PHARMACOGENETIC TESTING IN COMMUNITY PHARMACY TRIAL

Part II of the study will involve the cluster randomized trial to compare the effect of PGx testing as a stand-alone service to PGx testing with MTM (Figure 1/Aim 2)). We aim to enroll 20 pharmacist (in 20 separate pharmacies) and 360 patients in the study (~18 per pharmacy).

PGx Testing. Testing will be available for patients with active prescriptions for the drugs listed in Table 1. The drugs were selected based on CPIC guidelines and/or drug labels with PGx information that are likely to be filled at community pharmacies. If new CPIC guidelines are developed by the start of the study, we will update the list accordingly. Testing for each of the genes listed in the table will be provided by the CLIA-certified laboratory Pathway Genomics (CLIA # 05D1092505; San Diego, CA). The test for this study is a customized panel test that includes CYP2D6, CYP2C19, CYP2C9, SLC01B1 and VKORC1/CYP2C9. Currently, turnaround time for testing is 7-10 days. Given the varying coverage policies for PGx testing, all test fees will be supported by the study.

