and can read and write in English, and have a new or existing prescription (<1 year active) for a drug listed in Table 1 to be eligible to participate. Each pharmacy will identify existing patients eligible for testing through a query of their database for active prescriptions for the selected drugs. If more than 30 patients in a pharmacy are identified by the database search, we will ask pharmacists to contact patients with the newest prescriptions. Patients will be contacted by phone or in-person by the pharmacist to introduce the study. Interested patients will be asked to visit the pharmacy to learn more about testing, sign the consent form requested by the testing laboratory, and provide a DNA sample (buccal swab). Patients who have had PGx testing for one of the genes in Table 1 or had an MTM within the past 12 months will be ineligible. All women and minorities who meet the study inclusion criteria will be eligible to participate in the study. Based on our power calculations, we estimate that we would need to enroll 18 patients per cluster (360 total).

Patients who consent to testing based on their pharmacist's recommendation will be asked to provide a buccal swab for DNA extraction. Patient samples will be sent for testing to Pathway Genomics laboratory. Testing will be provided at no cost for participants. As the Pathway Genomics' clinical tests are currently available to any clinician, only the consent required by the testing lab will be required of the patient.

Patients in the control arms will be identified by each participating pharmacy; two controls will be identified per each participant in the PGx arms (2:1) and matched on drug, age and gender. Time on treatment, medication changes (dose/drug selection), and refill history (adherence) data will be collected along with demographic data and compared to patients in the PGx testing arms. Based on their pharmacy records, patients who have undergone MTM or PGx testing outside of the study will be excluded from the control arm.

Risk/Benefit Assessment. If patients decide to have pharmacogenetic testing, a buccal swab sample is required. There are no known risks to a buccal swab sample. The sample, or DNA extracted from the sample, will be sent to the laboratory and stored only for the time necessary laboratory regulations.

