The integration of PGx testing into the community pharmacy setting will be assessed primarily through surveys of patients and pharmacists. In addition, we will conduct semi-structured interviews with a subset of pharmacists to gather more in-depth understanding of their experiences, perceived barriers, and likelihood to continue to offer PGx testing. The measures to be assessed are described below; clinical outcome measures will be collected about the medications impacted by PGx only.

Patient Surveys (Aim 2b) The baseline survey will collect demographic data, prior knowledge about PGx, self-reported co-medications, time on treatment for PGx-related drug(s), and medication adherence (see Table 2; Appendix 5). The follow-up survey will gather data on 1) satisfaction with the testing experience in a pharmacy setting, including use/provision of patient materials from Aim 1; 2) perceived value of testing; and 3) comprehension of test result. Additional measures include medication-taking behaviors and information-sharing. The follow-up survey will be administered approximately one month after the PGx results are communicated since many of the medications are prescribed in 90-day allotments. Key survey questions are further described below; data on age, gender, co-medications, and time on treatment for PGx-related drug(s) will also be collected for controls.

- [Baseline] Literacy. We will screen for health literacy using the validated single question: “How confident are you filling out forms by yourself?” Compared to the gold standard literacy tools REALM or S-TOFHLA, this single question accurately predicts inadequate health literacy⁹⁹ and is more feasible to administer.
- [Follow-up] Comprehension of Results. Our primary outcome will be comprehension of test results based on gist recall of the phenotype.¹⁰⁰ Specifically, the outcome of interest is the patient’s recognition of the presence or absence of a variant gene. Due to the complexity of genotypes and presumed patient unfamiliarity with gene nomenclature, we do not believe it reasonable to expect patients to recall their genotype. Therefore, we will instead ask patients to circle their specific metabolizer status (e.g., rapid, extensive, intermediate, poor, or inconclusive). For the genes *SLCO1B1* and *VKORC1*, we will ask patients to indicate their test

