report found that they carried a known variant allele or not. We and others have used this approach to assess patient comprehension of genetic test results.^{101,102} The primary endpoint for comprehension is dichotomous (correct/incorrect). To assess patients' understanding of the significance of the result to their care, we will ask if the pharmacist recommended any changes to their treatment based on test result. Responses will be compared to the test results reported in the pharmacist's patient log (see below) and recommended pharmacist changes.

- **[Follow-up] Satisfaction with Testing Experience.** To assess patients' perceived value and satisfaction with PGx testing, we will ask about their likelihood to have PGx testing again in the community pharmacy setting. A survey tool from Walker et al.¹⁰³ will be adapted to gain further information about participant satisfaction. These questions have scale outcomes and will be treated as continuous variables.
- **[Follow-up] Perceived Value of Testing.** We will assess the perceived impact of the PGx test result on patients' confidence in the safety and effectiveness of the prescribed drug. A PGx result may be perceived as 'good' or 'favorable' if it is believed to inform selection of a safe drug or dosage adjustment. However, some patients may perceive the result as less than favorable if they are found to be a poor metabolizer and a lower dose is needed to reduce risk of side effects. Such patients may feel that the lower dose will be ineffective, and potentially fail to adhere to the drug regimen. In addition, we will assess participants' likelihood to pay for future PGx testing as a surrogate measure for perceived value.

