Patient Study Population. Patients will be invited to complete two surveys: 1) a baseline survey after they consent to testing and 2) a follow-up survey after they receive the test results. A brochure will be provided to the patient that will describe the purpose of the survey, risks and benefits, participant rights, investigator contact information, and how to access the survey. The pharmacist can ask if the patient would be willing to be contacted by the study coordinator or to complete the survey on their own time online. Upon completion of the baseline survey, participants will be asked to indicate if they would be interested in participating in the follow-up survey and re-contacted.

Pharmacist Study Population. Participating pharmacists will be invited to complete the baseline survey prior to the start of the in-person training session. The instructor (the clinical pharmacist on the research team) will describe the purpose of the survey, risks and benefits, participant rights, investigator contact information, and how to access the survey online (paper copy will also be available upon request). For the post-study interviews, pharmacists will be contacted at the completion of the study to ascertain interest to be interviewed.

Survey Administration. We will use Redcap, an online survey tool to design and administer the surveys. Redcap offers features that allow for custom designs, branching/skip logic, randomization of answer choices, multiple collection features and data output formats. A customized link will be sent to each participant to access the survey set, enabling the study coordinator to track and link responses between survey sets and to send reminders to only those who do not respond. Paper or phone option will be made available as requested; pharmacies can elect which method they prefer at the start of the study.

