Sensitivity analyses will be performed to examine the impact of reported changes in comprehension, as individuals who drop out could potentially be less likely to change behaviors. The results of complete case and imputed analyses will be reported. The type of missing data will be examined to understand whether they are missing at random (MAR) or not. If they are, then the assumption will be that the imputed analyses provide the better estimate of the treatment differences. If the decision is that one cannot say that the data were MAR, then both results will be presented with accompanying text describing the potential biases in both sets of results, the level and type of missingness seen, as well as the limitations of interpretations if a significant number of observations were missing.

STUDY SAFETY MEASURES

Safety Measures

This study does not contain any safety endpoint measures.

Pregnancy Guidelines

Pregnant females are eligible to participate in this study if they meet the inclusion criteria. There is no known risk to the mother or unborn child as a result of this study.

Safety Monitoring

Federal regulations require prompt reporting to the IRB, appropriate institutional officials, sponsor, coordinating center and the appropriate regulatory agency head of unanticipated problems involving risks to subjects or others that occur in the course of a subject's participation in a research study at DUHS. (45 CFR 46.103(b)(5)(i) and 21 CFR 56.108(b)(1)).

Investigators are responsible for monitoring the safety of patients who have entered this study and for alerting the study team to any event that seems unusual, even if this event may be considered an unanticipated benefit to the patient.

The Principal Investigator will continuously monitor and tabulate adverse events. Appropriate reporting to the Duke University Medical Center IRB will be made. The Principal Investigator or designee will also continuously monitor the conduct, data, and safety of this study to ensure that:

- Interim analyses occur as scheduled;
- Risk/benefit ratio is not altered to the detriment of the subjects;
- Appropriate internal monitoring of adverse events and outcomes is done;
- Over-accrual does not occur;
- Under-accrual is addressed with appropriate amendments or actions;
- Data are being appropriately collected in a reasonably timely manner.

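### The missing-data rule names a better estimate by deciding whether data are MAR, which the data cannot show, and no planned analysis varies the outcome assumed for non-responders

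*Combined protocol and SAP*

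**What the plan says.** The rule is in the last paragraph on survey data under Data Analysis. Complete-case and imputed analyses are both to be reported. Then: "The type of missing data will be examined to understand whether they are missing at random (MAR) or not". The consequence of a positive answer is: "If they are, then the assumption will be that the imputed analyses provide the better estimate of the treatment differences". If MAR cannot be asserted, the same two results are shown, with text on possible biases, the amount and kind of missingness, and the limits of interpretation. The section gives no criterion for the decision, no imputation model, and no analysis that departs from MAR in a stated way. The paragraph's stated motive is that people who drop out may be less inclined to change their behaviour. It describes the sensitivity analyses as meant to "examine the impact of reported changes in comprehension".

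The outcome at stake is set in Part III, Patient Surveys: "Our primary outcome will be comprehension of test results based on gist recall of the phenotype". It is scored as correct or incorrect and comes from the follow-up survey. Under Patient Study Population in Part III, that survey is optional: after the baseline survey, "participants will be asked to indicate if they would be interested in participating in the follow-up survey".

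**The concern.** Whether data are MAR or MNAR depends on the answers that were not given. Observed data can count against MCAR, for example if response varies with age or literacy. They cannot separate MAR from MNAR. The plan does not say what the examination will use. The candidates are the response pattern, the covariates and perhaps reasons for non-response, and none of these reveals the unseen answers. The step that decides which result is called better is therefore an analyst's judgement, made after the data are in and without a stated criterion.

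The second part matters more. The plan recognises that drop-outs may differ, but its response is either to prefer the imputed result or to show two results with narrative. Neither route tells the reader how different non-responders in one arm would have to be before the conclusion on the primary outcome changed. Response could plausibly differ by arm, since one arm has two MTM sessions and the other has testing alone. That is a reasoned risk, not something the documents establish.

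**Working it through.** **Inputs from the documents.** 20 pharmacies with about 18 patients each: 20 × 18 = 360, which matches the stated total. The endpoint is binary. The effect measure under Data Analysis is an odds ratio. The available text gives no expected non-response and no response rates by arm.

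**Assumptions for illustration.** Equal arms of 360 / 2 = 180; missing fractions of 10% to 30%; about 60% correct among PGx-only responders and 75% among MTM + PGx responders. Clustering is ignored, so these are point estimates only.

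**Formula.** Let r be the proportion correct among responders in an arm, m the missing fraction, and δ the difference between non-responders and responders. The arm's overall proportion is (1 − m)r + m(r + δ) = r + mδ. With T for MTM + PGx and C for PGx only, the risk difference moves from its δ = 0 value by m_T·δ_T − m_C·δ_C.

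**Size of the shift when δ applies in one arm only (percentage points):**

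| Missing | 10 points lower | 20 points lower | 30 points lower |
|---|---|---|---|
| 10% | 1 | 2 | 3 |
| 20% | 2 | 4 | 6 |
| 30% | 3 | 6 | 9 |

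**Equal in both arms.** With m = 0.3 and δ = −0.20 in each arm, the shift is −0.06 + 0.06 = 0.

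**Equal δ, unequal missingness.** With m_C = 0.30, m_T = 0.15 and δ = −0.20 in both, the shift is −0.03 + 0.06 = +0.03.

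**On the odds-ratio scale, 30% missing in each arm.** Responders are 126 per arm, with 76 correct (PGx only) and 94 correct (MTM + PGx). Every row fits these same observed counts.

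| Non-responders | PGx only | MTM + PGx | Risk difference | OR |
|---|---|---|---|---|
| As responders | 0.603 | 0.746 | 0.143 | 1.93 |
| 20 points lower, MTM + PGx only | 0.603 | 0.686 | 0.083 | 1.44 |
| 40 points lower, MTM + PGx only | 0.603 | 0.626 | 0.023 | 1.10 |
| 20 points lower, PGx only | 0.543 | 0.746 | 0.203 | 2.47 |
| 20 points lower, both arms | 0.543 | 0.686 | 0.143 | 1.84 |
| All counted incorrect | 76/180 = 0.422 | 94/180 = 0.522 | 0.100 | (94/86)/(76/104) = 1.50 |

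The extreme bounds on the risk difference have width m_T + m_C. They are 0.039 to 0.239 at 10% missing, −0.078 to 0.322 at 20%, and −0.200 to 0.400 at 30%.

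**Is comprehension measured more than once?** Table 2 lists it only in the follow-up survey. The baseline survey comes after consent to testing, before a result exists to be recalled. No change in comprehension can be calculated.

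**The case against.** Four points on the other side stand.

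First, a reader might infer that the rule lets an unfavourable result be dropped. The documents do not support that. Both results are reported whatever is decided, the MAR branch calls its preference an assumption, and the other branch prefers neither result and commits to discussing bias. MNAR is acknowledged, though not analysed.

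Second, a reader might infer that both planned analyses are valid only under MAR. No imputation method is stated, so this cannot be said of the imputed analysis. It is not generally true of the complete-case odds ratio either. Suppose true rates of 60% and 75% (OR = 3.0/1.5 = 2.0), with response of 80% if correct and 50% if incorrect in both arms. Responder odds are 0.48/0.20 = 2.4 and 0.60/0.125 = 4.8, so the ordinary odds ratio is still 4.8/2.4 = 2.0, although response is MNAR. When response depends on the outcome alone, bias needs that dependence to differ by arm.

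Third, the plan works to limit non-response: links that allow tracking, reminders to non-responders, paper or phone options, and $30 for the follow-up survey.

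Fourth, its stated worry concerns behaviour change, not comprehension directly, and the power calculations it mentions are not in the available text. It cannot be claimed that no dropout allowance was ever made.

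These points reduce the consequence. They do not make MAR decidable, and they do not supply an analysis of arm-dependent informative non-response.

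**Conclusion.** The concern holds in a limited form. The plan rests its preference between two estimates on a question the data cannot answer, and it plans no analysis that varies the outcome assumed for non-responders. The effect of the switch is confined to which result is labelled better.

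The size of the unexamined uncertainty depends on assumed figures. At 30% missing, a one-arm shortfall of 10 to 30 points moves the risk difference by 3 to 9 points. At 10% missing the same shortfalls move it by 1 to 3 points. With equal shortfalls and equal missing fractions the risk difference does not move, and in the illustration the odds ratio changes only from 1.93 to 1.84. A reader might infer that the trial's estimate will be biased by these amounts; the documents do not show that, because response rates and their relation to comprehension are unknown. This should be corrected before analysis, but it does not undermine the design. The reference to changes in comprehension is a minor wording error.

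**What to change.** 1. Delete the step that decides whether data are MAR. State MAR as a prespecified working assumption and name in advance which analysis, complete-case or imputed, is primary. Either can be defended.
2. Specify the imputation model. It should respect clustering by pharmacy and use a short list of baseline covariates, since 20 clusters of about 18 may not support a long one.
3. Whatever the missingness pattern, add a prespecified sensitivity analysis that shifts the log-odds of a correct answer among non-responders over a fixed grid, separately by arm. Include the case where missing counts as incorrect, and report the tipping point on the odds-ratio scale.
4. Replace the reference to changes in comprehension with comprehension at follow-up.

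The cost is revised analysis text and a few extra model runs, with no new data. The downside is that the sponsor may have to report a less favourable range.
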